## 10.0 CRITERIA FOR EVALUATION AND ENDPOINT DEFINITIONS

### 10.1 Recurrence

See [Section 9.0](#) for recurrence assessment schedule.

The following are the only acceptable criteria for renal cell cancer recurrence. Anything not listed as acceptable should not be an indication to alter protocol therapy. Any recurrence of malignant disease should be proven by tissue biopsy whenever possible. Supporting documentation must be submitted following diagnosis of renal cell carcinoma recurrence.

The following criteria of treatment failure constitute the only acceptable evidence of disease recurrence. Supporting documentation includes a copy of radiology and pathology reports.

Lung: (i) positive cytology or biopsy in the presence of a solitary lesion, (ii) radiologic evidence of multiple lesions felt to be consistent with metastases. (iii) neoplastic pleural effusion should be established by cytology or pleural biopsy.

Liver: (i) positive cytology or biopsy (ii) multiple new focal defects on MRI scan, CT or ultrasound that are enlarging in size as documented by repeat scans. (iii) proof of neoplastic abdominal ascites should be established by cytology or pleural biopsy.

Central Nervous System: positive brain CT scan or MRI scan or cerebral spinal fluid cytology.

Subcutaneous and Lymph Node Recurrence: (i) positive biopsy (ii) progressively enlarging solid mass or node(s) as evidenced by repeat CT or MRI scans (iii) ureteral obstruction in the presence of a mass as documented on CT or MRI scan.

Other Organs: (i) positive radiographic study and biopsy/aspiration cytology (ii) progressively enlarging solid mass or node(s) as evidenced by repeat CT or MRI scans.

Renal Bed: (i) positive radiographic study and biopsy/aspiration cytology (ii) progressively enlarging solid mass or node(s) as evidenced by two CT or MRI scans separated by at least a 4 week interval.

Skeletal: (i) positive radiographic study such as bone scan, (ii) for a solitary lesion or equivocal finding on scan, a biopsy is required to demonstrate recurrence, (iii) MRI or CT of solitary or equivocal lesion seen on bone scan that confirms metastasis is also acceptable.

### 10.2 Symptomatic deterioration

Global deterioration of health status requiring discontinuation of treatment without objective evidence of progression. Efforts should be made to obtain objective evidence of progression after discontinuation.

### 10.3 Performance Status

Patients will be graded according to the Zubrod performance status scale.

POINT	DESCRIPTION
0	Fully active, able to carry on all pre-disease performance without restriction.
1	Restricted in physically strenuous activity but ambulatory and able to carry out work of a light or sedentary nature, e.g., light housework, office work.
2	Ambulatory and capable of self-care but unable to carry out any work activities; up and about more than 50% of waking hours.
3	Capable of limited self-care, confined to bed or chair more than 50% of waking hours.
4	Completely disabled; cannot carry on any self-care; totally confined to bed or chair.

### 10.4 Recurrence-Free Survival

From date of registration to date of first documentation of recurrence outlined in [Section 10.1](#) or death due to any cause. Patients last known to be alive and recurrence-free are censored at date of last contact.

### 10.5 Time to Death

From date of registration to date of death due to any cause. Patients last known to be alive are censored at date of last contact.

## 11.0 STATISTICAL CONSIDERATIONS

### 11.1 Accrual Goal

ECOG's ASSURE trial randomized on average, 480 patients per year (40 per month). To be slightly more conservative, we anticipate that 28 patients per month (336 per year) will be randomized to this study. Based on the distribution of risk groups observed on **E2805** including half of the patients falling into the very-high risk group, it will be assumed that the placebo arm will produce a median recurrence-free survival of 4.9 years. **E2805** has also experienced a significant proportion of patients who have not completed the one year of protocol-specified treatment. Based on data from a recent amendment to **E2805**, twenty-five percent of patients have withdrawn from treatment on this study within the first three months. Although we expect everolimus to be better tolerated than sorafenib or sunitinib, we would estimate that about 15% of patients will stop protocol treatment within the first three months. Using a weighted average of the log hazard rates to obtain the effective hazard rate for the treatment arm under the alternative hypothesis, the ideal hazard ratio (HR) of 0.75 becomes an effective hazard ratio of 0.78 when lack of compliance is considered. Assuming exponential survival, 3.5 years of patient accrual, four additional years of follow-up and a sample size of 1170 patients (585 experimental, 585 placebo), the study has 85% power to detect a 22% reduction in the hazard rate of recurrence-free survival with everolimus compared to placebo (hazard ratio 0.78). This corresponds to an improvement in the median RFS from 4.9 to 6.3 years if the RFS

distributions are exponential. We will use a one sided stratified log rank test with  $\alpha = 0.025$ .

July 2015 Revision: As we now have a large amount of data to evaluate the rate of compliance to everolimus, we see that our original assumption of a 15% non-compliance rate was an underestimate. We propose to adjust the study design based on the observed compliance data from this trial in consultation with the study Data and Safety Monitoring Committee, and based on the following assumptions: those who receive less than 3 months of study drug have the same risk of recurrence as the placebo group, and those who receive 3-6 months of study drug have half the treatment benefit as those who receive more than six months.

We still assume an ideal HR=0.75, but we increase the accrual duration by one year to 4.5 years, and keep 4 years of follow-up. We are also reducing the statistical power from 85% to 80% in order to achieve a sample size that seems achievable within a reasonable amount of time. By making the prior assumptions about treatment efficacy, we will have an effective HR of 0.82 based on the proportion of dropouts and when they became noncompliant.

Assuming exponential recurrence-free survival, 4.5 years of patient accrual, four additional years of follow-up and an updated sample size of 1464 eligible patients (732 per arm), the study has 80% power to detect a 18% reduction in the hazard rate of recurrence free survival with everolimus compared to placebo (HR=0.82). This corresponds to an improvement in the median RFS from 4.9 to 6.0 years if the RFS distributions are exponential. We will use a one sided stratified log rank test with  $\alpha=0.025$ .

## 11.2 Analysis of Primary Endpoint

This study's design is based on assumptions about the accrual rate, the distribution of intermediate-high and very-high risk patients that have been randomized on ASSURE and histology. The total projected accrual adjusted for a 5% ineligibility rate is 1,537 patients (previously 1,218). If accrual to the intermediate-high risk strata reaches 50% of the total projected accrual then the stratum will be closed to further accrual. If accrual to the clear cell histology stratum reaches 85% of the total projected accrual then the stratum will be closed to further accrual. This will ensure accrual patterns in the strata with high event rates are comparable to those assumed in the study design. If the event rate information becomes available from ASSURE, the study team may consider recommending that the sample size be reevaluated. The sample size adjustment would be based on baseline characteristics. Only the number of patients accrued would possibly change, but the number of events and formal analysis timepoints, which are based on number of events, would not change.

The first interim analysis will be conducted after approximately 1,000 patients have been entered ( $n=500$  per arm), approximately 4 years after the study opens and when 30% of the expected number of recurrences have occurred on the placebo arm. A second interim analysis will be conducted approximately 5 years after the study opens and when 50% of the expected events on the placebo arm have been observed. The third interim analysis will be conducted when 70% of the expected events on the placebo arm have been observed. The fourth interim analysis will occur approximately 7.5 years after study activation when 90% of the expected events on the placebo arm have been observed. For each interim analysis, timing of analysis will be based on percent of expected information and not on calendar time. Evidence suggesting early termination of the trial and a conclusion that everolimus is not better than placebo would be if the alternative hypothesis of a 22% improvement in recurrence-free survival with the experimental arm is rejected at the 0.002 level. In addition, the null hypothesis of no difference in recurrence-free survival will be tested at the one-sided level of 0.001. If the decision is to continue the study to completion, the final analysis will be done after complete accrual

and approximately four years of follow-up at complete information when 804 total events have occurred across both arms. A stratified, one-sided log-rank test will be used for testing the primary hypothesis at the 0.022 level to account for interim testing.

December 2020 Update:

The expected endpoint rate in the placebo arm is lower than anticipated. Although three interim analyses have been conducted to date, the number of events is slowing making it difficult to reach the targeted number of events. Therefore, we consider some modification to the statistical analysis plan. This plan was developed by two independent biostatisticians who had not seen and had no access to endpoint data for this trial, with medical input from the primary study chair. The SWOG Data and Safety Monitoring Committee reviewed and approved this revision

The median recurrence-free survival of ASSURE (6.6 years) was longer than the six years assumed for this trial so the actual number of events in the placebo arm may be less than originally projected.

To keep power at 80% under current trial conditions, we continue to use the 4.5 years of accrual but allow 6 additional years of follow-up after the last accrual for a total of 10.5 years. Assuming a more conservative control arm hazard rate of 0.1027 (median RFS=6.75 years), the expected date of data maturity (804 total events) under the alternative hypothesis is September 2021. However, the necessary 804 events may never be attained because of drop out or failure of the underlying exponential distribution assumption and so the final analysis is expected in March 2022 even if 804 events have not been observed. In addition, the 4th and final interim analysis should be conducted one year prior in March 2021 regardless of the percent of expected information. The futility analysis is being changed from a one-sided 0.001 to a 1-sided value of 0.025 in the last interim analysis. This will have minimal effect on power if the true hazard ratio is 0.82 but would lead to earlier reporting if the observed hazard ratio is close to 1.0.

Updated Timing of Scheduled Analyses on **S0931, December 2020 Update**

Analysis	Estimated Study Time	# of Events on Placebo Arm* (% of total expected)	# of Events on Everolimus Arm (assuming Ha)	Testing Ho, Level of significance	Testing Ha, Level of significance
1 st interim analysis	4 years after activation	119 (30%)	104	.002	.001
2 nd interim	5 years after activation	208 (50%)	183	.002	.001
3 rd interim	6 years after activation	297 (70%)	264	.002	.001
4 th interim		March 2021		.002	.025
Final analysis		422 (100%)#	382#	0.022	N/A

\* timing of all planned analyses is based on the number of events in this column

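### Section 11.2 gives the interim levels for Ho and Ha one way in its text and the other way in its table (looks 1 to 3 for both, look 4 for Ho), and never states the futility alternative as a hazard ratio

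*Combined protocol and SAP*

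**What the plan says.** The interim-analysis paragraph of Section 11.2 gives two rules. The trial may stop with the conclusion that everolimus is no better than placebo "if the alternative hypothesis of a 22% improvement in recurrence-free survival with the experimental arm is rejected at the 0.002 level". For efficacy, "the null hypothesis of no difference in recurrence-free survival will be tested at the one-sided level of 0.001". The paragraph carries the revised accrual total of 1,537 and runs on into the 804-event final analysis, tested one-sided at 0.022. Nothing later in the section withdraws it.

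The December 2020 table in the same section lists .002 for testing Ho at each of the four interims. For testing Ha it lists .001 at looks 1 to 3 and .025 at look 4. The final row has 0.022 in the Ho column. The table does not give the sidedness of any level. The accompanying text says "The futility analysis is being changed from a one-sided 0.001 to a 1-sided value of 0.025 in the last interim analysis" and announces no change to the Ho level. It fixes look 4 at March 2021 "regardless of the percent of expected information".

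Section 11.1 holds two design effects. Under the original design, "the study has 85% power to detect a 22% reduction in the hazard rate of recurrence-free survival with everolimus compared to placebo" (HR 0.78). The July 2015 revision replaced this with 80% power for an 18% hazard reduction (HR 0.82), and adds: "This corresponds to an improvement in the median RFS from 4.9 to 6.0 years" under exponential distributions.

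**The concern.** These are the early-stopping thresholds of the primary endpoint. A reader who follows the text and a reader who follows the table apply different efficacy bounds at every interim and different futility bounds at looks 1 to 3. Someone auditing the three interims already done could not tell from the plan which rule should have been used.

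The futility alternative adds a second uncertainty. A 22% improvement can mean a 22% lower hazard (HR 0.78) or a 22% longer median (HR 0.82). The choice matters most at look 4, where the futility level was loosened to 0.025 and a futility stop is most likely.

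**Working it through.** **Inputs.** Table events at looks 1 to 3: 119+104 = 223, 208+183 = 391, 297+264 = 561. Final: 804 events, one-sided 0.022. Allocation is 1:1, so SE(log HR) ≈ 2/√D for D events.

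**The plan's own figure.** Events for 80% power at HR 0.82, one-sided 0.025: 4(1.960 + 0.842)²/(ln 0.82)² ≈ 798. With 804 events the power is 80.3%. The stated 804 events and 80% are reproduced.

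**Levels side by side.**

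| | Text | Table, looks 1–3 | Table, look 4 |
|---|---|---|---|
| Ho (efficacy) | 0.001, one-sided | .002 | .002 |
| Ha (futility) | 0.002, sidedness not stated | .001 | .025 |

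The December 2020 text gives the earlier futility level as one-sided 0.001. That is the table's value for looks 1 to 3, not the text's 0.002. The .025 at look 4 is an announced change and conflicts with nothing.

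**Efficacy bound**, exp(−z·2/√D), with z = 2.878 (0.002) or 3.090 (0.001):

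| Look | D | Ho 0.002 | Ho 0.001 |
|---|---|---|---|
| 1 | 223 | 0.680 | 0.661 |
| 2 | 391 | 0.747 | 0.732 |
| 3 | 561 | 0.784 | 0.770 |

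**Futility bound at look 3**, HR_alt·exp(z·2/√D), with HR_alt = 0.82: 1.064 at level 0.001, 1.046 at 0.002.

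**What 22% can mean.** Lower hazard: 1 − 0.22 = 0.78. Longer median: 6.0/4.9 = 1.22, and 1/0.82 = 1.22. The HR 0.78 design lengthened the median by 29% (6.3/4.9 = 1.29).

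**Look 4.** This look is set by date, so its event count is an assumption; 600 to 770 is used. The upper end follows from the plan's projection of 804 events in September 2021. An exponential model with 1,464 patients, control hazard 0.1027 and HR 0.82 gives about 67 events a year at that stage, so six months earlier the count is about 804 − 34 = 770.

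| D at look 4 | Efficacy, 0.002 / 0.001 | Futility at 0.025, HR 0.82 / HR 0.78 |
|---|---|---|
| 600 | 0.791 / 0.777 | 0.962 / 0.915 |
| 724 | 0.807 / 0.795 | 0.949 / 0.902 |
| 770 | 0.813 / 0.800 | 0.944 / 0.898 |

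**Type I error.** With independent increments, efficacy bounds only and a final level of 0.022, overall one-sided error is 0.0236 to 0.0242 with Ho at 0.002 and 0.0227 to 0.0230 with Ho at 0.001. The range covers look 4 at 600 to 724 events and a final analysis at 650 to 804.

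**Power at true HR 0.82**, table levels, futility treated as binding. The chance of a futility stop at any look is 2.6% if HR 0.82 is tested and 9 to 10% if HR 0.78 is tested. Power is 79.1% against 78.9% with look 4 at 724 events and the final at 804. The loss is 0.0 to 0.3 points when the final follows look 4 by 50 to 100 events, because most trials stopped this way would have failed anyway. It reaches 0.7 to 0.9 points only if 154 to 204 events accrue in the last year (650 or 600, then 804), against about 67 expected. Changing Ho from 0.002 to 0.001 costs about 0.2 points.

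**The case against.** **The levels could be reconciled by sidedness.** A two-sided 0.002 is a one-sided 0.001. The plan attaches one-sided to 0.001 in both places where its text gives that level and never to 0.002, and the table is silent. If .002 is two-sided throughout, text and table agree at looks 1 to 3, and on Ho at look 4. This reading cannot be excluded. Against it, the table's Ho column also holds 0.022, which the text calls one-sided, and one column would then mix two conventions without saying so.

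**A later, dated table exists**, in a revision approved by the monitoring committee, so there is a usable rule. That is fair, and it makes the table the natural authority. The text still states another Ho level.

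**The documents favour HR 0.82 for futility.** It is the current design alternative, the December 2020 text judges the futility change against a true HR of 0.82, and the revised medians give exactly 22%. This largely stands. A reader might infer that look 4 has no defined futility boundary, or that HR 0.78 is still being tested; the documents support neither. Two other hints settle nothing. The table's everolimus counts under Ha imply about HR 0.855 and match neither value. The expectation that the change "would lead to earlier reporting if the observed hazard ratio is close to 1.0" fits both bounds, since a value near 1.0 crosses either.

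**The consequences are small**, and the stopping rule guides the monitoring committee (Section 11.6) rather than binding it. Both are correct and limit the weight of the point.

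**Conclusion.** The text and table of Section 11.2 conflict as written: on Ho and Ha at looks 1 to 3, and on Ho at look 4. The levels in the text are probably transposed. That rests on the December 2020 sentence about the earlier futility level and on .002 being one-sided, as the 0.022 beside it suggests. The missing futility hazard ratio is a secondary gap in wording, with HR 0.82 the better-supported reading.

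The efficacy bound differs by about 0.01 to 0.02 on the hazard-ratio scale, and the look-4 futility bound by just under 0.05. A reader might infer that type I error is inflated or that power is materially lost. Neither follows: one-sided error is about 0.024 or 0.023, and power moves by about 0.3 points or less in plausible scenarios. Nor do the documents show that a completed interim was judged on the wrong threshold; they do not report what was applied. The problem is an unclear decision rule for the primary endpoint, and it should be fixed.

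**What to change.** Confirm from the three completed interim reports which Ho level, Ha level, sidedness and alternative hazard ratio were applied, and record any departure. Then make the text and table of Section 11.2 agree. If the table was applied, the text should give Ho 0.002 at each interim, Ha 0.001 at looks 1 to 3 and 0.025 at look 4, and 0.022 at the final analysis. State the sidedness in the table as well. Replace the 22% improvement by the hazard ratio tested for futility, which is HR 0.82 under the revised design, and say that it applies at look 4 too.

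The cost is a check of three existing reports, two corrected sentences and a sidedness label in the table. It needs no patients, no new data and no change to the overall alpha.

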# timing of final analysis at 804 total events or a maximum time of March 2022

11.3 Analysis of Secondary Endpoints

Secondary analyses will be performed for comparison between the two arms regarding survival and adverse events. With 732 patients on each arm, toxicity rates can be estimated to within at worst  $\pm 3.7\%$  (95% confidence interval). Additional exploratory analyses will include assessing the treatment effect within subgroups defined by the stratification factors as well as the interaction of everolimus with each of the stratification

factors, and whether the surgery was partial or a radical nephrectomy. With at least 15% of the patients having non-clear cell histology, for this subgroup the difference in the survival rates between the treatment arms can be estimated to within at worst  $\pm 5\%$  (95% confidence interval).

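### Section 11.2 gives two different H0 levels and two different futility hazard ratios for the fourth interim analysis; the 80% power also needs to be stated as conditional on about 804 events

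*Combined protocol and SAP*

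**What the plan says.** **Interim rules in the running text of section 11.2.** The trial may stop with the conclusion that everolimus is not better if the alternative, described as a 22% improvement in recurrence-free survival, is rejected at 0.002. H0 is tested at one-sided 0.001.

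**Interim rules in the December 2020 Update (section 11.2).** The timing table lists H0 at .002 for all four interims. It lists Ha at .001 for the first three and .025 for the fourth. The accompanying text says the futility level at the last interim moves from one-sided 0.001 to 0.025. It fixes that look at March 2021 whatever the information fraction, and reports that three interims have been conducted.

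**Effect size.** The July 2015 revision in section 11.1 replaces HR 0.78 by an effective HR of 0.82: "an updated sample size of 1464 eligible patients (732 per arm), the study has 80% power" for an 18% hazard reduction at one-sided 0.025. The update's comment on the cost of the futility change also refers to 0.82.

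**Final analysis.** The stratified log-rank test "will be used for testing the primary hypothesis at the 0.022 level to account for interim testing". The update opens its plan with "To keep power at 80% under current trial conditions, we continue to use the 4.5 years of accrual", adds six years of follow-up, and states that "the expected date of data maturity (804 total events) under the alternative hypothesis is September 2021". It then warns that "the necessary 804 events may never be attained because of drop out or failure of the underlying exponential distribution assumption", "so the final analysis is expected in March 2022 even if 804 events have not been observed". The footnote to the timing table repeats this: "timing of final analysis at 804 total events or a maximum time of March 2022".

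**The concern.** The interim levels decide whether the trial stops. For interims 1 to 3 the text and the table assign 0.001 and 0.002 to opposite hypotheses. For the fourth look, the one still to come under the update, the new .025 settles the futility level. The H0 level remains .001 in one place and .002 in the other.

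The futility hypothesis is also unsettled. The 22% in the text belongs to the design before July 2015. At a level of 0.001 or 0.002, the choice between 0.78 and 0.82 would seldom have mattered. At .025 the boundary is much closer to results the trial could plausibly produce, so the choice matters more.

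At stake is whether the monitoring committee has one prespecified rule. A result between the two readings would stop the trial under one and continue it under the other.

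A lesser issue is that 80% is the only overall power figure in the update, and the update also permits a final analysis below the event count to which that figure applies.

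**Working it through.** **1. The two sets of levels side by side (all one-sided)**

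| Look | H0, text | H0, table | Ha, text | Ha, table |
|---|---|---|---|---|
| Interims 1–3 | 0.001 | .002 | 0.002 | .001 |
| Interim 4 | 0.001 | .002 | 0.002, superseded by the update | .025 |
| HR tested for futility | – | – | 0.78 (22%) | not stated; revised design uses 0.82 |

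The update's description of the previous futility level as 0.001 agrees with the table and not with the running text.

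**2. Events at the fourth look.** The documents give no count for March 2021, so one has to be assumed. Inputs are exponential RFS, uniform accrual over 4.5 years, equal arms, control hazard 0.1027 and experimental hazard 0.82 × 0.1027 = 0.0842 (section 11.2 and HR 0.82), and no loss. Expected events in an arm of n patients at time T are n × [1 − (e^(−λ(T−4.5)) − e^(−λT)) / (4.5λ)].

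Taking September 2021 as the date of 804 events, six months earlier gives 773 events with 1,464 patients and 769 with 1,537. I use 770. For comparison, 90% of 804 is 724.

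**3. Boundaries.** The standard error of ln HR is 2/√D. At D = 770 it is 0.0721.

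- Efficacy: observed HR below exp(−z × 0.0721). With z(.002) = 2.878 this is 0.813. With z(.001) = 3.090 it is 0.800.
- Futility at .025: observed HR above HRa × exp(1.960 × 0.0721) = HRa × 1.152. This is 0.944 against 0.82 and 0.898 against 0.78.
- Chance of crossing if the true HR is 0.82: 2.5% against 0.82. Against 0.78 it is 1 − Φ(1.960 − ln(0.82/0.78)/0.0721) = 1 − Φ(1.266) = 10.3%.

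At 724 events the figures are 0.807 and 0.795 for efficacy, and 0.949 and 0.902 for futility, with crossing chances of 2.5% and 9.9%. The gaps are nearly the same.

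**4. Effect on error rates.** The first three looks are at 223, 391 and 561 events (both arms, from the table), and futility is treated as non-binding. With final counts from 804 down to 650 and an assumed fourth look before each, overall one-sided type I error with the final 0.022 is 0.0227 to 0.0241 under either set of H0 levels. The two H0 levels change power by about 0.2 points. The fourth-look futility rule costs under 0.4 points against either hazard ratio.

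**5. The plan's 80%.** Power = Φ(|ln 0.82| × √D/2 − z(α)), with |ln 0.82| = 0.1985. At D = 804 the first term is 2.813.

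- α = 0.025: Φ(2.813 − 1.960) = 80.3%, which reproduces the plan.
- α = 0.022: Φ(2.813 − 2.014) = 78.8%. Counting the interim efficacy looks gives 79.1% (H0 .002) or 78.9% (H0 .001).

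| Final events | 804 | 780 | 750 | 700 | 650 |
|---|---|---|---|---|---|
| Power at 0.022 | 78.8% | 77.6% | 75.9% | 72.9% | 69.7% |

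**6. Does the March 2022 cap bind?** On the dating in step 2, March 2022 brings about 834 events (1,464 patients) or 837 (1,537) without loss, so 804 would be reached first.

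**The case against.** The best defence of the interim rules is that the intention can be read. The table is the later text, it is headed as the December 2020 Update, and the update's own words agree with it on the earlier futility level. The 22% is probably leftover wording, since section 11.1 and the update both use 0.82. Error rates barely move. Most of this stands, and it limits the size of the problem. It does not remove it. The running text is still operative, the update does not restate the H0 level in words, and nowhere does it name the hazard ratio that the futility test uses. A committee should not have to infer a stopping boundary.

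On power, a reader might infer that the 80% is miscalculated, or that the March 2022 analysis will fall short. The documents support neither. The 80% reproduces at the design alpha of 0.025, and the gap at 0.022 is about one point. The plan openly says that 804 may not be reached, and it does not claim 80% for that case. On its own dating without loss there is about six months of margin. Any shortfall needs an assumed loss rate: about 0.9% per year with 1,464 patients or 1.1% with 1,537 on that dating, and other values if the calendar is anchored differently. The documents give no loss rate, and the September 2021 projection may already allow for dropout.

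**Conclusion.** The contradiction in the interim rules is real and should be resolved before the fourth look. At about 770 events, observed hazard ratios between 0.800 and 0.813 would stop for efficacy under the table but not under the text. Those between 0.898 and 0.944 would stop for futility against 0.78 but not against 0.82. If the true HR is 0.82, the chance of a futility stop at that look is about 10% rather than 2.5%. These boundaries rest on an assumed event count and shift slightly with it; the contradiction itself rests on no assumption.

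The consequences for error rates are small. Type I error stays below 0.025 under either reading, so the final 0.022 level is sound.

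The power statement is a minor point of wording. The figure holds to rounding at about 804 events, is about 79% at the level used, and declines gradually below that. The documents do not show that the cap will bind.

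**What to change.** Before the fourth interim:

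1. Bring the H0 and Ha levels in the running text of section 11.2 into line with the December 2020 table, so that one H0 level applies at the fourth look.
2. State that the futility test is against the revised design's HR of 0.82, or say explicitly if 0.78 is meant.
3. Leave the final 0.022 level as it is.
4. Reword the power statement as conditional on about 804 events (about 79% at 0.022). Optionally, add power at lower counts as tabulated above, and name the patient count (1,464 or 1,537), loss rate and follow-up time behind September 2021 and March 2022.

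The cost is a few sentences and, if wanted, one short table computed from design assumptions. It needs no added patients, no unblinded data and no change to the final test. The only downside is a slightly lower stated power.
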